## 8 STATISTICAL ANALYSES

We **hypothesized** that RaPPID will reduce the use of PPIs without a clinically meaningful increase in upper GI symptoms or upper GI complications such as bleeding.

**Primary outcome measure:** The **primary outcome** was the proportion of days PPIs are prescribed at or above the baseline daily dosing-frequency, over the 12 months following the index visit. We **hypothesized (H1)** that the proportion of days would be lower in intervention group than in the control group (i.e., that the outcome would be superior in the intervention vs control group). This outcome is analogous to the medication possession ratio. This was the appropriate measure of success of de-prescribing because it captured a variety of results in a single endpoint, including discontinuation without resumption, discontinuation with intermittent or on-demand use, and resumption of daily PPI at or above baseline dosing frequency. **Secondary outcome measures:** We also measured a variety of secondary outcomes to assess unintended, adverse events related to PPI de-prescribing. We hypothesize that utilization of outpatient care (H2) and the patient reported outcome (PRO) of upper GI symptoms (H3) will be non-inferior in the intervention vs control group.

**Utilization of outpatient and inpatient care:** Using CDW data, we assessed utilization of outpatient care – clinic visits or emergency department visits (using stop codes) for predefined upper GI symptoms/diagnoses (based on ICD-10 codes) or upper endoscopies (based on CPT codes). We also assessed use of inpatient care (i.e., hospital admissions) for predefined upper GI symptoms/diagnoses (based on ICD-10 codes).

**Upper GI symptoms and quality of life:** We assessed upper GI symptoms using the RDQ, a validated PRO instrument (30,31). We also measured generic quality of life using the SF-12 (32).

**Serious GI complications:** We assessed upper GI complications (bleeding, perforation, obstruction) using ICD-10 codes.

**PPI-related harms:** To ensure that we captured all relevant harms, we reviewed published observational studies of PPI harms to identify relevant diagnoses and ICD-9/10 codes.

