#### 8.1.2 VETERAN SURVEYS

Recruitment numbers were based on a power calculation in which patient-reported symptoms, as measured by the Reflux Disease Questionnaire, were treated as a continuous variable rather. Based on previous research, we assumed an RDQ score Standard Deviation (SD)=1.3 for GERD patients for this calculation. To detect the between-group difference of 0.71 vs. 1.13, assuming SD=1.3 with 90% power and alpha=0.01, we need 287 surveys completed per group (574 in total) at 3 months and 820 in total surveys returned at baseline to account for 30% dropout by month 3. We estimated a 50% response rate for the baseline survey and a 70% response rate for the follow-up survey. we mailed 1,722 baseline surveys and approximately 850 follow-up (3 month) surveys.

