## 8.3 STATISTICAL ANALYSES

Analyses proceeded in 3 phases. In the 1st phase, we examined the distribution of all study variables to assess extreme values, missing data, variances, possible coding errors, skewness, and type of distribution. In the 2nd phase, we evaluated bivariate associations between study arm and outcomes, as well as between each covariate and outcomes, using generalized linear models with generalized estimating equations to account for clustering. This was done to determine unadjusted measures of effect, assess possible confounders, and anticipate any collinearity in subsequent analyses. In the final phase, we fit multivariable models to identify the effects of the intervention.

Primary outcome (H1): To assess the primary outcome (proportion of days PPIs are prescribed), we used an intent-to-treat analysis with a mixed-effects model, with proportion of PPI days over 12 months as the dependent variable. The primary independent variable was study arm. Because randomization was done at the VISN (regional) level, we anticipated that patients seen at the same facility will show a positive intraclass correlation (ICC). The mixed-effects model accounted for such clustering by including VISNs as random intercepts. It also controlled for VISN strata variables used in randomization. We did not account for patient dropout since all data collection is done electronically and does not require further patient participation.

To assess secondary outcomes (utilization of outpatient care and upper GI symptoms patient reported outcomes), we used generalized linear mixed-effects models with logit link (hierarchical logistic regression) to account for VISN-level clustering and randomization strata. The primary independent variable was study arm. For each outcome, an odds ratio (OR) for adverse events in the intervention group relative to the control group was obtained from each logistic regression model, where a significant OR less than 1.0 will favor the intervention group. For analyses of the patient reported outcomes, the outcome of interest was the RDQ score assessed at 3 months. For both outcomes, non-inferiority was assessed by comparing the effect estimate and its 90% CI with a non-inferiority margin.

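### The upper GI symptom comparison (H3) is sized as a difference test on RDQ points but decided as a non-inferiority test on an odds ratio, against a margin with no stated value

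*Combined protocol and SAP*

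**What the plan says.** Section 8 sets out the overall hypothesis that the program lowers PPI use "without a clinically meaningful increase in upper GI symptoms or upper GI complications such as bleeding". It frames outpatient utilization (H2) and patient-reported upper GI symptoms (H3) as non-inferiority hypotheses.

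Section 8.1.2 sizes the survey. Symptoms, "as measured by the Reflux Disease Questionnaire, were treated as a continuous variable", give this calculation: "To detect the between-group difference of 0.71 vs. 1.13, assuming SD=1.3 with 90% power and alpha=0.01, we need 287 surveys completed per group". The section does not mention non-inferiority or a margin, and does not say whether alpha is one- or two-sided.

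Section 8.3 specifies mixed-effects models with a logit link for both outcomes, with an odds ratio for intervention against control. It names the 3-month RDQ score as the outcome for H3. The decision rule is one sentence: "For both outcomes, non-inferiority was assessed by comparing the effect estimate and its 90% CI with a non-inferiority margin". The readable text gives no margin in RDQ points or as an odds ratio, and no cut-point that would turn the RDQ score into a yes/no outcome.

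Two design facts bear on this. Section 6.2 says that nothing was blinded after randomization. Section 7.2.2 places the surveys in one VISN per arm.

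**The concern.** The sizing and the decision rule for H3 differ in three respects: the hypothesis (difference against non-inferiority), the error rate (alpha 0.01 against the one-sided 0.05 that a 90% CI implies) and the scale (mean RDQ points against an odds ratio). The documents reconcile none of them.

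A non-inferiority test without a margin has no defined null hypothesis, false-positive rate or power. H3 carries much of the claim that de-prescribing did not cost patients symptom control. If the margin is open when unblinded results become available, nothing in the text stops it being set where the data pass.

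**Working it through.** **Inputs (Section 8.1.2).** Difference d = 1.13 − 0.71 = 0.42; SD 1.3; power 90%; alpha 0.01; 287 per group. From Section 8.3: 90% CI, so one-sided 0.05. Assumed, because the documents give neither: a margin on the RDQ scale (0.42 and 0.30 are tried) and independent patients.

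**1. Reproduce the stated sample size.** n per group = 2 × SD² × (z_alpha + z_power)² / d².
- Two-sided 0.01: 2 × 1.69 × (2.576 + 1.282)² / 0.1764 = 285.1, so 286. The t-test version gives 286.8, so 287, as stated.
- One-sided 0.01: 2 × 1.69 × (2.326 + 1.282)² / 0.1764 = 249.4, so 250 (251 with t). This does not match.

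The plan's figure is therefore correct for a two-sided difference test. Two-sidedness is inferred from this match; it is not stated.

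**2. Standard error at the planned size.** SE = 1.3 × √(2/287) = 0.1085. The distance from the estimate to the upper 90% limit is 1.645 × 0.1085 = 0.179.

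**3. What the open margin does.** For an observed worsening of 0.20, the upper 90% limit is 0.20 + 0.179 = 0.38.
- Margin 0.42: 0.38 < 0.42, so non-inferior.
- Margin 0.30: 0.38 > 0.30, so not non-inferior.

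The largest observed worsening that passes is 0.42 − 0.179 = 0.24 in the first case and 0.30 − 0.179 = 0.12 in the second.

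**4. Power of a non-inferiority test at 287 per group.** With margin 0.42 and no true difference, power = Φ(0.42/0.1085 − z) = Φ(3.870 − z).

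| Interval | z | Power | n per group for 90% power |
|---|---|---|---|
| 90% CI | 1.645 | 98.7% | 165 |
| 95% CI | 1.960 | 97.2% | 202 |
| 99% CI | 2.576 | 90.2% | 286 |

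Under the 90% CI rule of Section 8.3, 90% power at no true difference goes with a margin of (1.645 + 1.282) × 0.1085 = 0.32, not 0.42. The stated 90% does not carry over to the planned decision rule.

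**5. Scale.** Steps 3 and 4 hold only for a mean difference in RDQ points. The model in Section 8.3 returns an odds ratio. Without a cut-point and a control-group proportion, 0.42 points cannot be converted, so neither the sizing nor the power applies to that model.

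**6. Limit of these figures.** The SE contains no between-VISN variance, and with one VISN per arm that variance cannot be separated from the program effect. As an illustration, suppose an RDQ intraclass correlation of 0.001 to 0.01 (assumed; none is given for the RDQ). The design effect 1 + 286 × ICC is then 1.286 to 3.86. When the true difference equals the margin, a nominal 5% rule based on the SE above passes Φ(−1.645/√1.286) = 7.3% to Φ(−1.645/√3.86) = 20.1% of the time.

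**The case against.** A 90% CI is the conventional one-sided 5% rule for non-inferiority. Nothing in the documents obliges a secondary outcome to use 99%, or to match the two-sided 0.05 of Section 8.1.1. This stands: the interval level is not wrong in itself.

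A reader might infer that, because the sizing uses 0.005 per tail and the decision rule 0.05, a harmful program would be called non-inferior ten times as often as the sizing implies. The documents do not support that. Section 8.1.2 is a difference calculation, and its alpha is the chance of declaring a difference when there is none; it sets no rate of false non-inferiority. Read as written, it implies that a true 0.42-point difference is missed 9.8% of the time. A 90% CI rule with margin 0.42 would pass such a program 5.0% of the time, which is less often. Ten is only 0.05/0.005. It needs a 99% CI non-inferiority design that the documents do not state, and it holds only where the true difference equals the margin. With margin 0.42, the ratio is 4.2 at a true difference of 0.30 and 41.7 at 0.60.

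Nor does the 90.2% for a 99% CI show that such a design was intended: the two calculations share one formula, so the match is automatic. Section 8.1.2 does not call 0.42 clinically meaningful and does not say which arm has which mean.

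Section 6.3 mentions a longitudinal mixed-effects model for the survey data, so a continuous analysis may have been meant. It names no link or effect measure, and Section 8.3 is explicit about the logit.

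Finally, figures are missing under Sections 8.1 and 8.1.1, so the absence of a margin is established for the readable text only. A margin chosen after the data is a possibility that the text leaves open, not documented conduct.

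**Conclusion.** The point holds as a mismatch between sizing and decision rule, together with a margin that has no stated value. The 287 per group is right for the test described in Section 8.1.2, but that is not the test in Section 8.3, so the planned H3 test has no stated power. The consequence is concrete: at the planned size, one result (a worsening of 0.20) is non-inferior or not according to a margin between 0.30 and 0.42 that the reader cannot find. H2 has the same gap, since its margin is not given either.

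The numbers rest on SD 1.3, 287 per group, an RDQ mean-difference scale and independent patients. The last assumption is optimistic with one VISN per arm. The conclusion that the two sections contradict each other on hypothesis, error rate and scale needs none of these assumptions.

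**What to change.** - In Section 8.3, analyse H3 as the difference in mean RDQ score at 3 months with a linear model, on the scale used for sizing.
- State a fixed margin in RDQ points, no larger than the 0.42 used for sizing, with its rationale and the date on which it was set.
- State one one-sided alpha for H3 and use it in both Sections 8.1.2 and 8.3. Keeping the 90% CI is acceptable if it is chosen explicitly.
- Restate the power for that test from step 4 of the working, and say that it ignores between-VISN variance with one VISN per arm.
- Give the H2 margin as a number on the odds-ratio scale.
- If no margin was fixed before outcome data were seen, report H2 and H3 as estimates with confidence intervals and make no non-inferiority claim. The document already carries final-report updates, so a margin first written down now could not be presented as prespecified.

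Cost: a change of model for H3, revised text in two sections and, if a stricter alpha is chosen, a wider reported interval. On the assumptions above, no more surveys are needed at margin 0.42 for any of the three interval levels; a smaller margin would lower the power.

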### 8.3.1 BASELINE DESCRIPTIVE STATISTICS

Intervention and control groups were compared on demographics of age, race, ethnicity, marital status, education, and Charlson Comorbidity Index (CCI).

## 9 SUPPORTING DOCUMENTATION

### 9.1 Regulatory, Ethical, and Study Oversight Considerations

Study documents were and will be retained in accordance with the Records Control Schedule (RCS) 10-1 which provides Veterans Health Administration (VHA) records retention and disposition requirements for VHA Central Office, Program Offices, and field facilities.

## 9.2 PROTOCOL DEVIATIONS

***Final report update: no SAEs were reported throughout the duration of the study.***

Because this was a minimal risk study with the intervention being implemented as part of VHA clinical operations and involving only use of paper and telephone surveys and telephone interviews about PPI de-prescribing experiences, we did not anticipate any serious adverse events (SAEs). Serious adverse events to be monitored included the following: 1) a breach of a participant's confidentiality or privacy that involved potential risk to that participant or others, 2) deviations from VA IRB regulations and policies, and 3) unanticipated problems (UAPs) that involved social or economic harm instead of the physical or psychological harm associated with adverse events. SAEs were prospectively tracked according to the following plan: reports of SAEs and protocol deviations were made by the study team member who discovered the event, the site PI, or site project manager (if applicable) to the primary site (Ann Arbor) project manager. The primary site project manager and PI would report the event to the Ann Arbor VA IRB (Primary Site IRB). Any SAEs and UAPs meeting the definition of serious would be reported within 5 business days of discovery to the Ann Arbor VA IRB. AEs and UAPs that did not meet the definition of serious were to be reported to Ann Arbor project manager as they were discovered, and would be reported to the Ann Arbor VA IRB in summary at the time of continuing review/project closure. Protocol deviations/violations that were likely to substantially adversely affect 1) the rights, safety, or welfare of a participant; 2) a participant's willingness to continue participation; or 3) the integrity of the research data, including VA information security requirements will all be reported within 5 working days of being made aware of the occurrence.

## 9.3 PUBLICATION AND DATA SHARING POLICY

This study will comply with all Department of Veterans Affairs regulations and policies.

## 9.4 CONFLICT OF INTEREST POLICY

***Final report update: no conflicts were reported throughout the duration of the study.***

The independence of this study from any actual or perceived influence was critical. Therefore, any actual conflict of interest of persons who had a role in the design, conduct, analysis, publication, or any aspect of this trial was disclosed and managed. Furthermore, persons who had a perceived conflict of interest was required to have such conflicts managed in a way that was appropriate to their participation in the design and conduct of this trial. The study leadership in conjunction with the Department of Veterans Affairs has established policies and procedures for all study group members to disclose all conflicts of interest and an established mechanism for the management of all reported dualities of interest.

## 9.5 ABBREVIATIONS AND SPECIAL TERMS

AE	Adverse Event
ANCOVA	Analysis of Covariance
BIA	Budget Impact Analysis
CAR	Clinical Analytics and Reporting
CBOC	Community Based Outpatient Clinic
CCMR	VA Ann Arbor Center for Clinical Management Research
CDW	Corporate Data Warehouse
CFIR	Consolidated Framework for Implementation Research
CFR	Code of Federal Regulations
CI	Confidence Interval

CKD	Kidney Disease
CLIA	Clinical Laboratory Improvement Amendments
CMCVAMC	Corporal Michael J. Crescenz VA Medical Center
CMP	Clinical Monitoring Plan
CMS	Centers for Medicare Services
COC	Certificate of Confidentiality
Co-I	Co-Investigator
COIN	Center of Innovation
CONSORT	Consolidated Standards of Reporting Trials
CPS	Clinical Pharmacy Specialist
CPT	Current Procedural Terminology
CRADO	Chief Research and Development Officer
CRF	Case Report Form
CSR&D	Clinical Science Research & Development
DART	Data Access Request Tracker
DCC	Data Coordinating Center
DHHS	Department of Health and Human Services
DSMB	Data Safety Monitoring Board
DRE	Disease-Related Event
EC	Ethics Committee
eCRF	Electronic Case Report Forms
ED	Emergency Department
EHR	Electronic Medical Records
FAC	Field Advisory Committee
FDA	Food and Drug Administration
FDAAA	Food and Drug Administration Amendments Act of 2007
FFR	Federal Financial Report
GCP	Good Clinical Practice
GEE	Generalized Estimating Equations
GERD	Gastroesophageal Reflux Disease
GI	Gastroenterology/Gastrointestinal
GLM	Generalized Linear Model
GLP	Good Laboratory Practices
GMP	Good Manufacturing Practices
GWAS	Genome-Wide Association Studies
H2RA	Histamine-2 Receptor Antagonist
HCUP	Healthcare Cost and Utilization Project
HIPAA	Health Insurance Portability and Accountability Act
HRQOL	Health-Related Quality of Life
HSR&D	Health Services Research & Development
IB	Investigator's Brochure
ICC	Intraclass Correlation Coefficient
ICD-9	International Classification of Diseases, Ninth Revision
ICD-10	International Classification of Diseases, Tenth Revision
ICH	International Council on Harmonisation
ICMJE	International Committee of Medical Journal Editors
IDE	Investigational Device Exemption
IDEAS	Informatics, Decision-Enhancement and Analytic Sciences Center
IHPI	Institute for Healthcare Policy and Innovation
IIR	Investigator Initiated Research
IND	Investigational New Drug Application

IOM	Institute of Medicine
IRB	Institutional Review Board
ISM	Independent Safety Monitor
ITT	Intention-To-Treat
LSMEANS	Least-squares Means
MedDRA	Medical Dictionary for Regulatory Activities
MI	Myocardial Infarction
MOP	Manual of Procedures
MUE	Medication Use Evaluation
NCRC	NCRC – North Campus Research Complex
NCT	National Clinical Trial
NSAID	Non-Steroidal Anti-Inflammatory Drug
NIH	National Institutes of Health
NIH IC	NIH Institute or Center
OHRP	Office for Human Research Protections
OR	Odds Ratio
OTC	Over-the-Counter
PBM	Pharmacy Benefits Management Services
PCP	Primary Care Provider
PD/PI	Project Director/Principal Investigator
PI	Principal Investigator
PIE	Partnerships for Implementation and Evaluation
PP	Per Protocol
PPI	Proton Pump Inhibitor
PRO	Patient Reported Outcome
PUD	Peptic Ulcer Disease
QA	Quality Assurance
QC	Quality Control
QOLRAD	Quality of Life in Reflux and Dyspepsia
QUERI	Quality Enhancement Research Initiative
QuEST	Qualitative Evaluation for Systematic Translation
RAPID	VA Office of Reporting, Analytics, Performance Improvement, and Deployment
RAPPID	Randomized Proton Pump Inhibitor De-Prescribing Program
RA	Research Assistant
RDQ	Reflux Disease Questionnaire
RCT	Randomized Controlled Trial
RE-AIM	Reach Effectiveness Adoption Implementation Maintenance Framework
RR	Relative Risk
RRP	Rapid Response Proposal
SAE	Serious Adverse Event
SAP	Statistical Analysis Plan
SD	Standard Deviation
SDR	Service Directed Research
SF-12	Short Form Health Survey (12 Items)
SMC	Safety Monitoring Committee
SOA	Schedule of Activities
SOC	System Organ Class
SOP	Standard Operating Procedure
UP	Unanticipated Problem
US	United States
TDF	Theoretical Domains Framework

VA	Veterans Affairs
VAAAHS	VA Ann Arbor Healthcare System
VACHS	VA Connecticut Healthcare System
VAMedSAFE	VA Center for Medication Safety
VAPSHCS	VA Puget Sound Health Care System
VASLC	VA Salt Lake City Healthcare System
VERAM	Veterans Education and Research Association of Michigan
VHA	Veterans Health Administration
VISN	Veterans Integrated Service Network
VREC	Veteran Research Engagement Council

## 9.6 PROTOCOL AMENDMENT HISTORY

Version	Date	Description of Change	Brief Rationale
1.0	4/26/2019	Randomization changed from facility level to VISN level	Operational partner decision based on feasibility of implementation of intervention

